597 2. Participants can be withdrawn from the trial at the discretion of the Investigator due to
 598 safety concerns of if judged to be non-compliant with the trial protocol.

599 3. Pregnancy or intention of becoming pregnant

600 4. If target treatment dose of the randomized product is not tolerated by the subject.

601 5. If the trial investigator suspects acute pancreatitis, the trial drug will be discontinued until
 602 the confirmatory tests (clinically indicated laboratory and imaging) have been conducted
 603 and appropriate treatment has been administered. We anticipate confirmation within 72
 604 hours. If acute pancreatitis is confirmed, the participant will be withdrawn from the trial.
 605 If acute pancreatitis is not confirmed, the participant will resume the trial drug at the
 606 same dose previously used before temporary discontinuation.

607 6. Temporary trial drug discontinuation criteria:
 608 - Side effects to trial medication (until such side effects have resolved or have
 609 been otherwise addressed)
 610 - Acute illness requiring treatment or hospitalization
 611 - The longest time that the subject can be off trial drug and still continue in the trial
 612 is 4 weeks. If the trial drug is discontinued for >72 hours, then the dosing
 613 escalation regimen will be restarted at 0.6 mg daily and titrated up according to
 614 prescribing information recommendations.

616 **Subject Replacement**

617 Participants will not be replaced if they withdraw or become ineligible but they will be asked to
 618 return at the end of the trial period to complete the follow-up imaging/laboratory testing and
 619 analyzed in an intention to treat analysis. As up to a 28% drop-out rate is anticipated, enrolment
 620 will account for expected drop-out to minimize loss to follow-up given that subjects will not be
 621 replaced.

623 **Rationale for Trial Population**

624 The trial population represents the target population for which liraglutide is approved for chronic
 625 weight management in adult patients, with the additional inclusion criterion of a diagnosis of
 626 metabolic syndrome. This important criterion has been selected to enrich the trial population
 627 with participants with a high visceral adipose tissue burden in order to improve the statistical
 628 power to observe a meaningful effect on visceral adipose mass and enrich the trial population
 629 with individuals at high risk for cardiovascular disease.

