809 Background medication should be withheld on the day of the fasting Visits 1, 3, and 16 until
 810 blood sampling has been done. At all other visits the background medication and trial product
 811 should be taken as usual during the conduct of the trial.

812

813 Trial product will be dispensed at visits 3 through 15. Subjects will be asked to bring all empty,
 814 partly used and unused trial product at visits 4 through 16 for drug accountability. The
 815 computerized randomization system should be contacted for trial product dispensing. If the
 816 subject attends the clinic for a visit not described in the protocol, then an Unscheduled Visit
 817 Form must be completed. The Unscheduled Visit Form should not be completed if the sole
 818 purpose of the visit is trial product dispensing. If an unscheduled visit is made for the purpose of
 819 dispensing trial products to the subjects then an unscheduled dispensing session must be
 820 completed in the computerized randomization system. If it is not possible to attend the visit
 821 within the visit window, the subjects should be called in for an Unscheduled Visit.

822

823 In case a subject is being prematurely withdrawn from the trial before or at visit 16, the
 824 Investigator will ensure that the procedures for the End of Treatment visit (Visit 16) are

825 undertaken, if possible. The primary reason (adverse event, non-compliance with protocol or
826 other) for discontinuation will be specified in the CRF and a computerized randomization system
827 withdrawal session should be completed. Even if the subject is not able to attend a final visit, the
828 End of Trial Form (EOT) must be completed.

829
830 Subjects that have discontinued the trial prematurely before Visit 16 will be asked to attend a
831 visit (Visit 16x) taking place 40 weeks after the randomization date. The purpose of this visit will
832 be recording of all outcome assessments if possible. If the subject is not willing to attend Visit
833 16x, it should be documented in the patient medical record that the subject has refused to
834 attend the visit.

835
836 **Visit 1**
837 At Visit 1, the informed consent will be reviewed again for signature and participants will be
838 screened for eligibility in the trial. This will include interview assessment for inclusion and any
839 exclusion criteria and laboratory components of the metabolic syndrome. Subjects that meet all

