 912 dose will be gradually escalated to 3.0 mg starting with 0.6 mg and with a dose level increment
 913 of 0.6 mg every 7 days.

914

915 If the subject is not eligible for randomization, the subject is considered a screening failure and
 916 the subject will be registered as a screening failure in the computerized randomization
 917 system.

918
 919 At this visit, they will undergo all baseline anthropometric, imaging, and laboratory assessments.
 920

921 **The following will be recorded in the CRF:**

- 922 • Age
- 923 • Sex
- 924 • Race/ethnicity
- 925 • Weight
- 926 • Height
- 927 • Concomitant medications
- 928 • Blood Pressure
- 929 • Pulse
- 930 • Waist Circumference
- 931 • Hip Circumference
- 932 • Visceral adipose tissue mass
- 933 • Abdominal subcutaneous adipose tissue mass
- 934 • Total fat mass
- 935 • Total fat-free mass
- 936 • Lower body adipose tissue mass
- 937 • Hepatic fat content
- 938 • Laboratory tests, including
 - 939 - Markers of insulin resistance: fasting blood glucose, insulin
 - 940 - Markers of inflammation: CRP
 - 941 - Lipids: TG/HDL-C ratio,
 - 942 - Natriuretic peptides: NT-proBNP

943
 944 **Visits 4-7**

945 At Visits 4-7, subjects will follow a dose escalation regimen and trial staff will monitor for AEs
 946 and ensure adherence to diet and exercise recommendations. Subjects will follow a fixed dose
 947 escalation. The dose will be gradually escalated to 3.0 mg starting with 0.6 mg and with a dose
 948 level increment of 0.6 mg every 7 days.

949

950 **Visits 8-15**

951 Visits 8-15 are the maintenance phase of the trial. Subjects will attend visits with trial staff every
 952 4 weeks to ensure adherence to the trial protocol, monitor for AEs, monitor for non-adherence to
 953 trial medication, and monitor adherence to diet and exercise recommendations.

954

955 **Visit 16**

956 Visit 16 is the final visit during the maintenance phase during which follow-up imaging and
 957 laboratory studies will be assessed in addition to assessments done during Visits 8-15. All
 958 remaining doses of trial medication will be collected at this visit and returned to Novo Nordisk.
 959 No further trial drug will be administered after this visit.

960

961 **The following will be recorded in the CRF:**

- 962 • Weight

- 963 • Height
- 964 • Concomitant medications
- 965 • Blood Pressure
- 966 • Pulse
- 967 • Waist Circumference
- 968 • Hip Circumference
- 969 • Visceral adipose tissue mass

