1074 collected. Subjects will be advised with regards to the best possible post-trial treatment options
1075 for their weight management and metabolic syndrome. These treatments will be at the
1076 discretion of the local Investigator. Unblinding will occur at LPLV and after ascertainment of
1077 primary and secondary endpoints.

1078

1079

1080 **Premature discontinuation**

1081 If the trial subject opts for early trial termination, he/she will be asked to attend a premature trial
1082 discontinuation visit at the time of discontinuation. The purpose of this visit will be to assess
1083 body weight, occurrence of AEs and discuss end of trial imaging studies. The PI will offer end of
1084 trial imaging to assess for the primary and secondary efficacy endpoints if the subject has
1085 completed at least 40 weeks of trial treatment. Every effort will be made to assess for AE and
1086 SAEs during the trial for all patients including those prematurely withdrawing from the trial.

1087

1088 **TRIAL DRUGS AND MATERIALS:**

1089 Treatment with liraglutide or placebo will be blinded to the subjects and investigators throughout
1090 the trial.

1091

1092 **Trial medication(s) / devices(s)**

1093 The administration of liraglutide/ placebo will be as outlined above.

1094 The following trial products will be supplied by Novo Nordisk, Denmark.

- Liraglutide 6.0 mg/mL, 3 mL pen-injector for subcutaneous injection
- Placebo 3 mL pen-injector for subcutaneous injection

1095 Liraglutide will be available at a concentration of 6.0 mg/mL. Liraglutide and placebo will be
1096 supplied in a 3 mL pen-injector . Correct dosing is achieved by using the dose counter and the
1097 dose pointer to see how many mg to select. The subject will hear a "click" every time they turn
1098 the dose selector. The dose will not be set by counting the number of clicks the subject hears.
1099 Dosing with the liraglutide/ placebo pen-injector is controlled by turning the dose selector until
1100 the dose indicator shows the relevant dose (0.6, 1.2, 1.8, 2.4 or 3.0 mg, respectively or
1101 placebo). Therefore, the dose level (injection volume) of liraglutide or placebo is open labeled.

1102

1103

1104

1105

1106 Liraglutide or placebo is administered once daily by subcutaneous injections with the pen-
1107 injector, either in the abdomen, thigh or upper arm. Injections can be done at any time of day

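### The premature-discontinuation rule offers the end-of-trial MRI to voluntary leavers only after 40 weeks on treatment, which early leavers cannot reach and two other sections do not require

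*Protocol*

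**What the plan says.** Three parts of the protocol tell staff what to do about imaging when a subject leaves early.

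- **Premature discontinuation.** The section opens: "If the trial subject opts for early trial termination, he/she will be asked to attend a premature trial" discontinuation visit. That visit covers body weight, adverse events and a discussion of the final imaging. The investigator will then offer end-of-"trial imaging to assess for the primary and secondary efficacy endpoints if the subject has" "completed at least 40 weeks of trial treatment".
- **Subject Replacement.** Participants who withdraw or become ineligible are not replaced. They are asked to "return at the end of the trial period to complete the follow-up imaging/laboratory testing and" are to be "analyzed in an intention to treat analysis". No minimum time on treatment is given.
- **Visit Procedures.** At premature withdrawal the Visit 16 procedures are to be done if possible. Subjects who stopped before Visit 16 are also asked to attend a "visit (Visit 16x) taking place 40 weeks after the randomization date", whose purpose will "be recording of all outcome assessments if possible". Again there is no minimum time on treatment, and a refusal must be documented.

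Three other places fix the context. Trial type gives 40 weeks on treatment. The Visit 16 section says: "No further trial drug will be administered after this visit". The visit schedule with assessments places the visceral fat MRI at randomization and at end of treatment only.

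**The concern.** The first rule attaches a condition to the imaging offer that the subjects it addresses cannot satisfy. The other two rules make the same request to the same subjects without that condition. Nothing in the protocol ranks the three, and the section on premature discontinuation is where a coordinator would naturally look when a subject opts out.

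The primary endpoint is at stake. Visceral fat has one post-baseline measurement, so a week-40 scan that is not offered leaves the subject without any observed primary outcome. The subject will usually remain in the full analysis set, because one post-baseline value of any efficacy endpoint is enough and weight is measured from Visit 4 onward. The primary analysis is by intention to treat, so that subject must then be imputed or dropped. Either way, the observed data come more heavily from those who completed treatment. A statistical analysis plan cannot recover a scan that was never offered.

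**Working it through.** **1. Can an early leaver meet the condition?**

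- Required time on treatment: 40 weeks × 7 = 280 days.
- Visit 16 is at 40 weeks ± 3 days (visit schedule): days 277 to 283. Drug stops at that visit.
- A subject who leaves before the window opens has at most 276 days of treatment: 276 / 7 = 39.4 weeks, below 40.
- A subject who leaves within the window, or between Visit 16 and Visit 17 (week 42), could reach 280 days, but is due for the Visit 16 scan in any case.

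The condition therefore excludes the early leavers for whom the offer would matter and admits only those for whom it adds nothing.

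**2. Could 40 weeks mean time since randomization?** Visit Procedures counts Visit 16x from the randomization date and says so. Premature discontinuation counts weeks of trial treatment. As written these are different clocks.

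**3. The rules side by side, for a subject who opts out at week 20 (illustration):**

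| Section | Week-40 MRI |
|---|---|
| Premature discontinuation | Condition for the offer not met (20 < 40 weeks) |
| Subject Replacement | Asked to return for imaging |
| Visit Procedures | Asked to attend Visit 16x for all outcomes, if possible |

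**4. How many subjects could be involved?** The plan's own figures reproduce:

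- Inputs (Sample Size Calculation and Statistical Methods): difference 8 percentage points, SD 16, two-sided alpha 0.05, power 80%, 1:1 allocation.
- The t-test calculation for a standardized difference of 8 / 16 = 0.5 gives 63.77 per arm, rounded up to 64, so 128 in total. Power at 64 per arm is 80.1%.
- Allowing for 28% loss: 128 / (1 − 0.28) = 177.8, so 178 randomized.
- Expected loss from all causes: 0.28 × 178 = 49.8, about 50 subjects.

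The 28% is a single all-cause allowance. The protocol does not say how many of these subjects would leave by their own choice, which is the only group that Premature discontinuation addresses. So 50 is a ceiling and not an estimate.

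**The case against.** The strongest reply is that retrieval is already planned. Visit Procedures covers everyone who stops before Visit 16, with no exception for those who opt out, and Subject Replacement repeats the request and names imaging. The conditional sentence says *if*, not *only if*, and prohibits no scan. Its own visit is meant to discuss final imaging with leavers, which would make little sense if almost none could have it. A slip for 40 weeks after randomization is plausible.

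Much of this stands. A reader might infer that every voluntary leaver's scan will be lost. The documents do not support that, because two sections instruct the opposite and staff may follow them. What does not stand is that the conflict is therefore harmless: a condition on an offer tells staff when to make it, and two of the three instructions cannot be followed together with the third. If a slip is the explanation, the correction is the same.

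Three further inferences should also be resisted.

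- **Loss of planned power.** The trial is sized on 128 completers after 28% loss, so up to about 50 missing scans are already allowed for. The issue is how complete the intention-to-treat data are, not power.
- **Missing data that cannot be handled.** The Missing Data section names multiple imputation and sensitivity analyses and leaves the detail to the analysis plan. Imputation could use baseline visceral fat and the interim weights. It is still a substitute for a scan that could have been requested.
- **Opting out leaves follow-up permission intact.** The Withdrawal Criteria separate withdrawal of follow-up permission from stopping the drug. They do not say that leaving the trial leaves that permission in place. The contradiction rests on Subject Replacement and Visit Procedures alone.

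**Conclusion.** The point holds as an inconsistency that is wrong as written. Read literally, the imaging condition under Premature discontinuation cannot be met by anyone who leaves before the Visit 16 window, and it conflicts with two sections that ask the same subjects to return for imaging. It bears on the primary endpoint because there is no other post-baseline visceral fat scan.

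The size is bounded but not known: at most about 50 of 178 subjects (28%), and fewer to the extent that exits are not voluntary, that staff follow Visit Procedures, or that leavers decline the scan. The loss arises only where staff apply the conditional sentence.

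A reader might also infer a bias for or against liraglutide. The protocol gives no rate of voluntary leaving by arm for this trial, so no direction can be claimed. Exits imposed by the protocol, such as intolerance of the target dose, fall outside the conditional sentence and are already covered by Visit 16x.

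**What to change.** Under Premature discontinuation, delete the condition that the subject has "completed at least 40 weeks of trial treatment". State instead that the end-of-trial MRI is offered at Visit 16x, 40 weeks after randomization, regardless of time on trial drug, unless the subject withdraws permission for follow-up. If 40 weeks was meant as the timing of the scan, this wording says so.

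The cost is one sentence of protocol text. Visit 16x and its assessments are already planned, so no new visit or procedure is added. The rules on when trial drug is stopped need no change.

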1108 irrespective of meals. However, it is preferable that liraglutide be injected during the same

1109 overall time period on a day to day basis. Subjects will be instructed to perform an air shot
 1110 before the first injection with the pen-injector. For further information, please see the direction
 1111 for use (DFU) for the liraglutide pen-injector. These DFUs will be provided together with the trial
 1112 product. The Investigator or trial staff will instruct subjects in how to inject liraglutide or placebo,
 1113 and will ensure that the subjects are familiar with the DFU. It will be documented in the subject's
 1114 research record that the subject has been instructed in the use of the pen-injector.

1115
 1116 Subjects will follow a fixed dose escalation and in order to reduce the level of side effects,
 1117 liraglutide is gradually escalated up to the maintenance dose. Subjects will be instructed to
 1118 escalate the liraglutide (active or placebo) dose to 3.0 mg/day over a 4 week period following an
 1119 initial dose of 0.6 mg/day and weekly dose escalation steps of 0.6 mg/day.

1120 If subjects do not tolerate an increase in dose during dose-escalation, the Investigator will have
 1121 the option to delay the next dose escalation for approximately one week. All subjects must be at
 1122 the target dose 3.0 mg or placebo at the latest 8 weeks after randomization.

1123
 1124 Dose escalation schedule:

Week	Dose (mg)
0	0.6
1	1.2
2	1.8
3	2.4
4 and beyond	3.0

1125
 1126 After reaching the target dose, 3.0 mg liraglutide or placebo dose and dosing frequency should
 1127 not be changed at any time during the treatment period. If any dose is missed by the subject up
 1128 to and including 3 consecutive days it will be documented in the research record and the
 1129 Investigator will discuss the importance of treatment compliance with the subject. After a
 1130 potential discontinuation up to 3 days the subject must be re-initiated on trial drug on target
 1131 dose 3.0 mg liraglutide or placebo. Missed doses for more than 3 consecutive days will be
 1132 discussed with the PI and it will be up to Investigator's judgment if the subject can continue on
 1133 target dose or should be withdrawn.

1134
 1135 It is always important that the Investigator emphasizes to subjects the necessity of compliance
 1136 with regard to taking trial drug as described in the protocol. It is the responsibility of the

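### For a subject on 3.0 mg who is off drug for more than 72 hours and stays in the trial, one protocol section restarts at 0.6 mg and another allows only 3.0 mg

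*Protocol*

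**What the plan says.** **Interruptions over 72 hours.** Protocol, Withdrawal Criteria, item 6, deals with temporary stops and names side effects and acute illness. It then sets two limits: "The longest time that the subject can be off trial drug and still continue in the trial" "is 4 weeks. If the trial drug is discontinued for >72 hours, then the dosing" schedule begins again at 0.6 mg daily and goes up as the prescribing information recommends.

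Protocol, Trial Drugs and Materials, Trial medication(s) / devices(s), also covers gaps. For a subject who has reached 3.0 mg, the dose should "not be changed at any time during the treatment period. If any dose is missed by the subject up" (the line runs on into the rule for short gaps). After a "potential discontinuation up to 3 days the subject must be re-initiated on trial drug on target" dose. Missed doses for longer than 3 consecutive days are to be "discussed with the PI and it will be up to Investigator's judgment if the subject can continue on" "target dose or should be withdrawn".

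**Suspected pancreatitis that is ruled out.** Withdrawal Criteria, item 5, expects the answer within 72 hours and returns the subject to the dose taken before the stop. The drug section says that such a subject may stay in the trial with titration started again.

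**Time limit on escalation.** The drug section requires every subject to be at "the target dose 3.0 mg or placebo at the latest 8 weeks after randomization".

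**The concern.** Two current sections tell staff to give different doses to the same subject, and nothing in the protocol says which one governs. Whoever follows one section departs from the other.

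This is first a dosing-safety matter. The drug section gives its own reason for stepping the dose up: "Subjects will follow a fixed dose escalation and in order to reduce the level of side effects". Item 6 ties the restart to the prescribing information. Continuing at 3.0 mg after a gap of up to 4 weeks skips both safeguards, and the investigator who would prefer to re-titrate is not given that choice in the drug section.

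It is also a matter of consistency, because two subjects with the same gap could be handled differently depending on which page was consulted. Such gaps are foreseeable. Item 6 plans for them, and the section Tolerability and Adverse Events reports nausea in 47.6% and vomiting in 16.5% on 3.0 mg in an earlier trial. Those are event rates, not interruption rates.

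**Working it through.** The protocol states no figure here to reproduce. The check is a comparison of the rules, followed by arithmetic on the escalation schedule.

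**1. Do the rules meet on the same event?** Dosing is once daily, so 3 days = 3 x 24 = 72 hours. The counts may differ slightly according to whether one starts from the last dose taken or the first dose missed. Four or more missed daily doses trigger both rules on either count.

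**2. The rules side by side, for a subject on 3.0 mg who stays in the trial**

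| Event | Withdrawal Criteria | Trial medication(s) / devices(s) |
|---|---|---|
| Off drug more than 72 hours, up to 4 weeks | Item 6: restart at 0.6 mg | Continue at 3.0 mg |
| Pancreatitis ruled out within 72 hours | Item 5: same dose, 3.0 mg | Titrate again |

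Withdrawal is open to the investigator under both sections, so the conflict concerns only subjects who continue. In the second row the drug section also disagrees with itself, since its rule for gaps of up to 3 days gives 3.0 mg.

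**3. Size, active arm only.** Inputs: the dose escalation schedule in the drug section (0.6, 1.2, 1.8, 2.4, then 3.0 mg). Item 6 refers to the prescribing information, which is not among the documents. Weekly 0.6 mg steps after a restart are therefore an assumption.

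- First dose after the gap: 3.0 / 0.6 = 5-fold.
- Next 28 days after a restart: 7 x (0.6 + 1.2 + 1.8 + 2.4) = 7 x 6.0 = 42 mg.
- Next 28 days when continuing: 28 x 3.0 = 84 mg, twice as much.

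**4. The week-8 limit.** A restart on day R reaches 3.0 mg on day R + 28. The limit is day 8 x 7 = 56.

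- A subject who reached 3.0 mg on day 28 has already met the limit, and a later restart does not breach it.
- For a subject still in the first escalation, R + 28 <= 56 requires R <= 28. Take a one-week delay at every step, which puts the subject at 1.8 mg on day 40, and a 4-day gap from day 40. The restart is on day 44 and the target is reached on day 72, which is 72 - 56 = 16 days late although every rule was followed. This is a narrow case.

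**5. Late restarts.** Week 40 is day 280. The last restart that reaches 3.0 mg by then is on day 280 - 28 = 252, which is week 36. A restart at week 38 (day 266) is only at the 1.8 mg step on day 280.

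**The case against.** The best reply is that the two sections address different causes: item 6 lists side effects and acute illness, while the drug section speaks of missed doses in a paragraph about compliance. The drug section does use the word discontinuation, but only in its sentence on gaps of up to 3 days. Its opening also says that administration follows what was set out earlier, which could be taken to import item 6.

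This softens the conflict without removing it. The drug section limits its rule to no cause, and a subject stopped for illness for 10 days has also missed more than 3 days of doses. A general reference back does not override a specific instruction that offers two outcomes, neither of them a restart. Investigator judgment does not close the gap either, because it is a choice between those same two outcomes.

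Other parts of the reply stand:

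- A reader might infer that items 5 and 6 also contradict each other when a pancreatitis work-up lasts, say, 5 days. Read in order they largely fit: item 5 expects an answer within 72 hours, and item 6 takes over beyond that.
- A reader might infer that any restart after day 28 breaches the week-8 limit. That is wrong for subjects who have already reached 3.0 mg.
- The dose contrasts do not apply to the placebo arm, and the 28-day totals depend on weekly steps.
- Re-titrating after a short pancreatitis work-up is the more cautious option. The objection to it is that another item says the opposite.

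**Conclusion.** The point holds for subjects on 3.0 mg who are off drug for more than 72 hours and up to 4 weeks and remain in the trial. Item 6 gives them 0.6 mg, while the drug section offers 3.0 mg or withdrawal. A second, separate mismatch exists for pancreatitis ruled out within 72 hours. In the active arm the first dose after a long gap differs five-fold, and with weekly steps the next 28 days differ by 42 against 84 mg.

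It is tempting to go on to say that the conflict harms subjects or weakens the primary comparison. The documents support neither. They give no rate of interruptions over 72 hours and no measure of the harm of resuming 3.0 mg after a gap. The rules apply equally, and under blinding, to both arms. No effect on power or on the week-40 MRI endpoint is claimed. The conflict should be corrected because it changes what subjects are given and is cheap to remove; it does not invalidate the trial.

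**What to change.** Make Withdrawal Criteria, item 6, the single rule and carry it through.

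- **Drug section, gaps over 3 days.** Replace the option of continuing on target dose with: *After more than 72 hours and up to 4 weeks off trial drug for any reason, a subject who continues in the trial restarts at 0.6 mg and is re-titrated as in the escalation schedule.* Add to the sentence barring dose changes: *except for a restart under this rule.* The investigator's right to withdraw a subject is unchanged.
- **Pancreatitis ruled out.** State one rule in item 5 and in the drug section: resume the previous dose if off drug for 72 hours or less, restart at 0.6 mg if longer. This matches how the drug section treats every other gap of up to 3 days. If the sponsor prefers the cautious option of always re-titrating, both places should say so.
- **Week-8 limit.** State that it applies to the first escalation only and does not apply to a subject restarted under this rule.
- **More than 4 weeks off drug.** Stop trial drug and follow Visit Procedures: Visit 16 procedures if possible, and Visit 16x at week 40.

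The cost is one short amendment and a note in staff training, with no extra visits or subjects. The downside is that restarted subjects spend about 4 weeks below 3.0 mg, which item 6 already accepts. Those restarted after week 36 do not reach 3.0 mg before the week-40 MRI.
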